6.2.2 Treatment period

The first trial drug administration should occur as soon as possible after the randomization / treatment allocation. A treatment cycle is defined as 28 days. If initiation of a subsequent cycle is delayed due to medical reasons, visits beyond Day 28 may be necessary. Additional unscheduled visits may be performed at the Investigator's discretion if medically indicated, but at least weekly; these unscheduled visits should also be reported in the eCRF.

An End of Cycle (EOC) visit will be performed at the end of each treatment cycle, i.e. on Day 29 (± 3 days). A subsequent treatment cycle should not start earlier than on the 29th day of the precedent cycle (if e.g. the previous cycle started on a Tuesday the next cycle will start earliest on a Tuesday 4 weeks later).

Day 29 (Visit 4, EOC) can be the same day as Day 1 (Visit 1) of the next treatment cycle if the patient is eligible to receive further treatment without delay. In that case Day 29 becomes Day 1 of next cycle and all procedures and assessments as indicated for Day 29 and Day 1 of the next cycle should be performed.

During Phase I and Phase II the decitabine treatment schedule for Cycles ≥ 2 will be individually customized depending on the blast count at the end of previous cycle. For details on the treatment schedules refer to [Table 4.1.3.1: 1](#) for patients treated in the Phase I Dose Escalation and to [Table 4.1.3.2: 1](#) for patients treated in the Phase I Extension and Phase II.

Refer to [Section 4.1.4.2](#) for treatment delay and resuming subsequent cycle of treatment.

With the aim to minimize the burden for trial participants, after approval of Protocol version 7.0, the mandatory protocol procedures are reduced for all patients who continue to receive trial medication in treatment cycles >7 . Refer to updated [Flow Chart](#) for specific requirements during treatment period.

During the treatment phase, patients will receive trial drug administration in cycles of 28 days. Day 1 of each cycle is defined as the start day of decitabine administration of that cycle. Patients will receive administration with BI 836858 once weekly, i.e. every 7 days usually on Day 1, 8, 15 and 22 of each cycle. However, independent of the trial phase, the very first administration of BI 836858 for each patient receiving the combination treatment will take place on Day 8 (or Day 9 at the latest) of Cycle 1, and then onwards in weekly intervals. Whenever possible the weekly intervals between two administrations of BI 836858 and the 4-weekly intervals between the start dates of decitabine treatment on Day 1 of two subsequent cycles should be respected. For further details on the administration schedule of BI 836858 please refer to [Section 4.1.4](#).

[REDACTED]

Bone marrow aspirations (and biopsies if medically indicated) for local response assessment are also required at the end of Cycle 1 (Day 29 \pm 3), at the end of Cycle 2 and every other cycle thereafter (**after approval of Protocol version 7.0, BM assessments will be done at investigator's discretion only**). The BM sample collection at the end of Cycle 2 is not a mandatory trial procedure in patients with $\geq 5\%$ blasts in peripheral blood. From Cycle 2 onwards, BM samples can be taken up to 7 days before the scheduled visit 4 (EOC), i.e. between Day 22 and 29 of the treatment cycle) unless the patient has achieved CR in which case further bone marrow aspiration/biopsies are not required unless clinically indicated; earlier response assessments can be performed based on peripheral blood count recovery.

For patients with CR who receive maintenance treatment (patients who were switched from weekly to monthly infusions with BI 836858 and have completed one treatment cycle of maintenance treatment) and for patients with CR in Phase II treatment Arm II (receiving

decitabine monotherapy) the weekly visits on Day 8, 15 and 22 may be adjusted according to the patient's medical condition at the investigator's discretion. Weekly visits may be skipped, but it is recommended to continue with visits in bi-weekly intervals.

6.2.2.1 End of treatment visit (EOT)

The EOT visit will be performed as soon as possible but no later than one week (7 days) after permanent discontinuation of trial medication(s) for any reason, or when the Investigator decided with the patient to permanently discontinue the trial medication.

The following parameters and investigations will be obtained and/or performed:

- Safety laboratory parameters and urine analysis as specified in [Section 5.3.6](#)
- Physical examination including weight (may be completed up to 2 days prior) and ECOG performance score
- Vital signs at time points specified in [Section 5.3.5](#)
- Serum pregnancy test in women of childbearing potential
- 12-lead ECG
- Adverse events (AEs)
- Changes in concomitant therapies
- Number and type of transfusions, if applicable
- [REDACTED]
- [REDACTED]
- Bone marrow aspirate and peripheral blood for disease assessment (only in patients who did not end treatment due to PD or relapse and who did not have a bone marrow aspirate within the past four weeks, or if PD is suspected but not cytologically confirmed)
- Documentation of End of trial treatment. This will include the reason for conclusion of trial (if applicable), premature discontinuation of trial, and date of last administration of the trial drug.
- In case the patient receives further anti-cancer treatment: regimen, drug name and start and stop dates

With the aim to minimize the burden for trial participants, after approval of Protocol version 7.0, the mandatory protocol procedures at EOT are reduced for all patients who continue to receive trial medication in treatment cycles >7. Instead, assessments should be performed at the investigator's discretion, based on standard medical care. Refer to updated [Flow Chart](#) for specific requirements during treatment period.

6.2.2.2 End of Residual Effect Period visit (EoR)

The REP is defined in [Section 5.3.9](#). The End of REP (EoR) visit should not be performed earlier than 30 days after permanent discontinuation of the trial medication. The information collected at this visit should include all new reportable AEs that occurred after EOT and a follow-up of adverse events ongoing at EOT.

The following parameters and investigations will be obtained and/or performed:

- Date and type of contact
- Vital Signs
- Safety laboratory parameters only if not within normal range at EOT
- 12-lead ECG only if abnormal at EOT and pathological findings were not present at baseline
- Follow-up of adverse events in case they were not yet recovered at EoT visit
- Documentation of concomitant medications only if indicated for treatment of adverse events
- In case the patient receives further anti-cancer treatment: regimen, drug name and start and stop dates

With the aim to minimize the burden for trial participants, after approval of Protocol version 7.0, the mandatory protocol procedures at EoR visit are reduced for all patients who continue to receive trial medication in treatment cycles >7. Instead, assessments should be performed at the investigator's discretion, based on standard medical care. Refer to updated [Flow Chart](#) for specific requirements during treatment period.

6.2.3 Follow-up Period and Trial Completion

6.2.3.1 Extended follow-up period

6.2.3.1.1 Follow-up of Phase I Patients

Patients in the Phase I part will be followed-up for approximately 6 months after the EOT visit, irrespective whether a patient progressed on treatment or not. The first follow-up visit will be performed approximately 3 months and the second follow-up visit approximately 6 months after the EOT visit. Completion of the second follow-up visit will define the individual patient's end of trial participation (also refer to [Section 6.2.3.2](#)).

The following information will be collected during the follow-up visits and documented in the eCRF:

- Date and type of contact
- Vital Status: Collect information on progression or relapse, death, lost to follow-up
- Follow-up of adverse events in case they were not yet recovered at EoR visit
- In case the patient receives further anti-cancer treatment: regimen, drug name and start and stop dates

After approval of Protocol version 7.0, no further follow-up visits will be carried out. The last visits of an individual patient after withdrawal from trial treatment will be the EoR visit.

6.2.3.1.2 Follow-up of Phase II Patients

Patients in the Phase II part will be followed-up for overall survival at 3 monthly intervals until death, lost to follow-up or completion of the whole trial (as specified in [Section 6.2.3.3](#))

whatever occurs earlier. For all patients, irrespective whether a patient progressed on treatment or not, the follow-up period for overall survival starts 3 months after the EOT visit. These visits may also be performed by e.g. telephone interview or via written correspondence in case the patient is unable to visit the Investigator.

The following information will be collected during the follow-up for survival period and documented in the eCRF:

- Date and type of contact
- Vital Status : Collect information on progression or relapse, death, lost to follow-up
- Follow-up of adverse events in case they were not yet recovered at EoR visit
- In case the patient receives further anti-cancer treatment: regimen, drug name and start and stop dates

6.2.3.2 Trial completion for an individual patient

A patient is considered to have completed the trial in case any of the following applies:

- Completion of planned follow-up period including extended follow up (for patients in the Phase I part approximately 6 months after EOT; patients in the Phase II part will be followed-up for vital status until death)
- Lost to follow-up
- Refusal to be followed-up
- Death
- Decision of the Sponsor to end the trial (refer to [Section 6.2.3.3](#))

6.2.3.3 End of the whole trial

The end of the trial will be defined as when both of the following have occurred:

- 1) All **entered and treated** patients have discontinued trial drug.
- 2) The last patient has completed the EoR visit.

In the case that the trial is ended by the Sponsor when patients are still being treated and the final report of the trial is being prepared, the patients will either be included in a follow-up trial or alternatively kept on treatment in this trial. Those patients will then be reported in a revised report and it will be noted in the original report that such a revised report will be written.

7. STATISTICAL METHODS AND DETERMINATION OF SAMPLE SIZE

7.1 STATISTICAL DESIGN - MODEL

7.1.1 Phase I Dose Escalation

The primary objective of the Phase I Dose Escalation part is to determine the MTD of BI 836858 in combination with an intensive 10 day treatment schedule of decitabine. To determine the MTD, patients are entered sequentially into escalating dose cohorts. The dose-finding will be guided by a Bayesian 5-parameter logistic regression model with overdose control [\[R13-4806\]](#), [\[R13-4803\]](#), [\[R15-4233\]](#).

In the following, DLT denotes a dose-limiting toxicity occurring during the first treatment cycle.

The 5-parameter logistic regression model is defined as follows. Let $\pi_{1,d1}$ be the probability of having a DLT when giving dose d_1 of BI 836858, and $\pi_{2,d2}$ the probability of having a DLT when giving dose d_2 of decitabine, respectively. A logistic regression is used to model the dose-toxicity relationship for each of these drugs individually:

BI 836858: $\text{logit}(\pi_{1,d1}) = \log(\alpha_1) + \beta_1 \log(d_1/d_1^*)$

Decitabine: $\text{logit}(\pi_{2,d2}) = \log(\alpha_2) + \beta_2 \log(d_2/d_2^*)$

Here, the doses $d_1^* = 160 \text{ mg}$ and $d_2^* = 20 \text{ mg/m}^2$ represent the reference doses for BI 836858 and decitabine, respectively.

Under independence, the probability of a DLT when giving the combination dose d_1, d_2 is obtained as

$$\pi_{12,d1,d2}^0 = \pi_{1,d1} + \pi_{2,d2} - \pi_{1,d1}\pi_{2,d2}$$

with corresponding odds

$$\text{odds}(\pi_{12,d1,d2}^0) = \pi_{12,d1,d2}^0 / (1 - \pi_{12,d1,d2}^0).$$

In order to account for a potential positive (higher toxicity than expected under independence) or negative (lower toxicity than expected under independence) interaction between BI 836858 and decitabine, a dose-dependent interaction term $-\infty < \eta < \infty$ is introduced in the model:

$$\text{odds}(\pi_{12,d1,d2}) = \text{odds}(\pi_{12,d1,d2}^0) \exp(\eta d_1/d_1^* d_2/d_2^*)$$

and $\pi_{12,d1,d2}$ is used in the likelihood

$$r_{d1,d2} \sim \text{Binomial}(n_{d1,d2}, \pi_{12,d1,d2})$$

where $r_{d1,d2}$ denotes the number of DLTs observed in $n_{d1,d2}$ patients at dose combination d_1, d_2 .

Since a Bayesian approach is applied, prior distributions f for each of the parameter vectors $\theta_1 = (\log(\alpha_1), \log(\beta_1))$, $\theta_2 = (\log(\alpha_2), \log(\beta_2))$ and for the interaction term η need to be specified.

Proprietary confidential information © 2019 Boehringer Ingelheim International GmbH or one or more of its affiliated companies

The prior distributions for θ_k ($k=1,2$) will be specified as a mixture of two bivariate normal distributions,

$$f(\theta_k) = a_{1,k} f_1(\theta_k) + a_{2,k} f_2(\theta_k)$$

with $a_{1,k}, a_{2,k}$ the prior mixture weights ($a_{1,k} + a_{2,k} = 1$) and

$f_i(\theta_k) = \text{MVN}(\mu_{ik}, \Sigma_{ik})$ ($i=1,2$) a bivariate normal distribution with mean vector μ_{ik} and covariance matrix Σ_{ik} where

$$\Sigma_{ik} = \begin{pmatrix} \sigma_{ik,11}^2 & \sigma_{ik,11}\sigma_{ik,22}\rho_{ik} \\ \sigma_{ik,11}\sigma_{ik,22}\rho_{ik} & \sigma_{ik,22}^2 \end{pmatrix}$$

Mixture prior distributions have the advantage that they allow for specification of different logistic dose-toxicity curves, therefore making the prior more robust.

A weakly-informative normal prior distribution will be used for η .

The estimated probability of DLT at each dose level from the model will be summarized using the following intervals:

Under dosing: [0.00, 0.16)

Targeted dosing: [0.16, 0.33)

Over dosing: [0.33, 1.00]

The BLRM-recommended dose for the next cohort is the level at which the probability for the target dosing interval is maximal out of the dose candidates satisfying the overdose control criterion: $P(\text{over dosing}) < 25\%$.

However, the maximum allowable dose increment for the subsequent cohort will be no more than 100% of previous dose levels.

The MTD may be considered reached if the following criteria are fulfilled:

1. The posterior probability of the true DLT rate in the target interval [0.16, 0.33] of the MTD is above 0.50, OR
2. At least 15 patients have been treated in the study, of which at least 6 were treated at the MTD.

The SMC may recommend stopping the dose finding phase after the criterion for MTD is fulfilled. Further patients may be included to confirm the MTD. If no DLT is observed at a dose of which the efficacy is considered sufficient, the SMC may decide to include additional patients at this dose level and to declare this dose as the RExP1D.

Prior derivation

To determine the prior distributions for $(\log(\alpha_1), \log(\beta_1))$ and $(\log(\alpha_2), \log(\beta_2))$, a meta-analytic predictive (MAP) approach will be used. For BI 836858 toxicity information from the ongoing 1315.1 Phase I study will be used. For decitabine toxicity information from three

Proprietary confidential information © 2019 Boehringer Ingelheim International GmbH or one or more of its affiliated companies

published studies will be incorporated. The historical data used for BI 836858 and decitabine can be found in Table 7.1.1: 1 and Table 7.1.1: 2 respectively.

Table 7.1.1: 1 Historical data for BI 836858

Study	Dose [mg]	N of patients with DLT during Cycle 1 / N of patients
1315.1 ⁽¹⁾		
	10	0/3
	20	0/3

⁽¹⁾ Using data after the clinical hold. Trial 1315.1 is still ongoing.

Table 7.1.1: 2 Historical data for decitabine

Study	Dose	N of patients with DLT during Cycle 1 / N of patients
Issa et al 2004 [R11-1101] ⁽¹⁾		
	n.a. ⁽¹⁾	7/50
Blum et al 2007 [R15-4796] ⁽²⁾		
	n.a. ⁽²⁾	3/25
Blum et al 2010 [R12-3308] ⁽³⁾		
	20 mg/m ² (10 day schedule)	7/53

- (1) Phase I study of low-dose prolonged exposure schedules of decitabine in hematopoietic malignancies: No DLTs were reported for this study. The number of DLTs was therefore approximated by the number of non-haematological AEs of CTCAE grade 3 and 4 that would also constitute a DLT in the present trial; data from all investigated decitabine doses and dosing schedules was used: 5x10, 10x10, 15x10, 20x10, 15x15, 15x20, 15x10 [mg/m² x days]
- (2) Phase I study of decitabine alone or in combination with valproic acid in AML: No DLTs were reported for this study. The number of DLTs was therefore approximated using the number of non-haematological AEs (possibly attributable to decitabine or valproic acid) of CTCAE grade ≥ 3 overall cycles that would also constitute a DLT in the present trial. Furthermore, the reported average number of treatment cycles was used to approximate the number of DLTs during the first treatment cycle. Data from all investigated decitabine doses was used: 15 mg/m² x 10 days; 20 mg/m² x 10 days
- (3) No DLTs were reported for this study. The number of DLTs was therefore approximated using the number of non-haematological AEs of CTCAE grade ≥ 3 experienced during the first two cycles of treatment that would also constitute a DLT in the present trial.

The following steps were used to derive the prior distributions for all parameters:

1. $\log(\alpha_1), \log(\beta_1)$:
 - a. The meta-analytic-predictive prior was derived using the information in [Table 7.1.1: 1](#), allowing for moderate between-trial heterogeneity. This mixture component was assigned 90% mixture weight.
 - b. A second, weakly-informative component was added with 10% mixture weight.
2. $\log(\alpha_2), \log(\beta_2)$:
 - a. The meta-analytic-predictive prior was derived using the information in [Table 7.1.1: 2](#), allowing for substantial between-trial heterogeneity. This mixture component was assigned 90% mixture weight.
 - b. A second, weakly-informative component was added with 10% mixture weight.
3. η : based on the a priori assumption of no interaction between the two compounds (but with considerable uncertainty for interaction), a normal distribution with mean 0 and standard deviation 0.993 was chosen.

A standard deviation of 0.993 allows for a 7-fold increase/decrease in the odds($\pi_{12, d1^*, d2^*}$) of a DLT at the dose combination d_1^*, d_2^* compared to the odds($\pi_{12, d1^*, d2^*}^0$) of a DLT at (d_1^*, d_2^*) with no interaction between the two compounds. For example, if the true DLT rate under no interaction, i.e. $\pi_{12, d1^*, d2}^0$, was 0.2 (odds = 1/4), the upper 97.5% quantile for the DLT rate (allowing for interaction) would be 0.63636 (odds=7/4). This corresponds to considerable uncertainty for interaction.

The prior distributions are given in [Table 7.1.1: 3](#). The corresponding prior probabilities of a DLT at different doses and the corresponding probability of under-dosing, targeted dosing and overdosing are shown in [Table 7.1.1: 4](#). As can be seen from Table 7.1.1: 4, the combination of 20 mg BI 836858 with 20 mg/m² decitabine has a prior probability of overdosing < 25%. It fulfils the overdose criterion and is therefore a suitable starting dose combination.

Table 7.1.1: 3 Summary of prior distributions

	Prior Component	Mixture Weight	Mean	SD	Correlation
BI 836858	MAP	0.9	(-1.395, 0.337)	(1.826, 0.959)	0.306
	Weakly inf.	0.1	(-1.395, 0.337)	(2.000, 1.000)	0.000
Decitabine	MAP	0.9	(-1.883, -0.0004)	(0.633, 1.042)	-0.003
	Weakly inf.	0.1	(-1.883, -0.0004)	(2.000, 1.000)	0.000
¶	n.a.	n.a.	0	0.993	n.a.

Table 7.1.1: 4 Prior probabilities of DLT at selected doses

Dose BI 836858 [mg]	Dose decitabine [mg/m ²]	Probability of true DLT rate in			Mean	SD	Quantiles		
		[0, 0.16)	[0.16, 0.33)	[0.33, 1]			2.5%	50%	97.5%
20*	20	0.483	0.384	0.133	0.202	0.146	0.040	0.164	0.640
40*	20	0.420	0.394	0.186	0.228	0.165	0.042	0.183	0.714
80	20	0.335	0.353	0.312	0.283	0.202	0.043	0.226	0.820
160	20	0.230	0.232	0.537	0.413	0.277	0.034	0.364	0.954
320	20	0.209	0.126	0.665	0.564	0.355	0.011	0.618	>.999

* Doses with asterisk meet the overdose criterion (P(over-dosing) < 0.25)).

The prior distribution may be updated once the trial has started if new relevant data become available. The prior distribution that is used in the BLRM for the purpose of the SMC's determination of the next dose level will be documented in the SMC meeting minutes. Details on the prior distribution for the final analysis will be given in the trial statistical analysis plan (TSAP).

Statistical model assessment

The model was assessed using two different metrics:

1. Hypothetical data scenarios: for various potential data constellations as they could occur in the actual trial, the maximal next doses as allowed by the model and by the 100% escalation limit are investigated. Data scenarios thus provide a way to assess the “on-study” behaviour of the model.
2. Simulated operating characteristics: these illustrate for different assumed true dose-toxicity relationships, how often a correct dose would be declared as MTD by the model. They are a way to assess the “long-run” behaviour of the model.

In summary, the model showed very good behaviour as assessed by these metrics. More details can be found in [Section 10.2](#).

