5.3.3 Recommended Phase II Dose (RP2D)

Before the conclusion of Phase I and prior to initiating the Phase II, up to 30 patients will receive the combination treatment of BI 836858 at MTD (or RExP1D if applicable) and decitabine in one of the two extension cohorts.

If deemed necessary by the Sponsor and the SMC, there will be an option to open further Dose Escalation cohort(s) following the extension cohorts to determine the RP2D, based on additional biomarker, PK/PD and safety data.

Based on the overall Phase I data, the SMC will make a final determination of the RP2D, which must not exceed the MTD. The Phase I safety analysis report or lean interim CTR, including the rationale of RP2D determination will be sent to competent authorities/ethic committees and made available to all participating Investigators prior to the initiation of Phase II.

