For each of these scenarios, 1000 trials were simulated. It was then assessed how often a dose was declared as MTD with true DLT rate in the under-, targeted or over-dosing range. Furthermore, the average, minimum and maximum number of patients per trial and the average number of DLTs per trial are reported. Results are shown in Table 10.2: 3.

Table 10.2: 3

Simulated operating characteristics

Scenario	% of trials declaring the MTD with true DLT rate in				# Patients	# DLTs
	Underdose	Target dose	Overdose	Stopped		
1: Prior	0.0	79.8	1.3	18.9	12.40 (3 - 27)	2.96 (1 - 8)
2: HighTox	0.0	45.3	22.1	32.6	11.12 (3 - 30)	3.14 (1 - 8)
3: Low Tox	68.8	29.8	0.0	1.4	17.21 (3 - 36)	2.07 (1 - 7)
4: Low-High	24.6	68.5	5.5	1.4	15.42 (3 - 39)	2.44 (1 - 7)

In Scenarios 1 and 4, more than 60% of the simulated trials correctly declared the MTD as a dose with true DLT rate in the target interval [0.16, 0.33].

Namely, in scenario 1, which reflects the case that the true dose-toxicity is aligned with prior means, 79.8% of the simulated trials declared the MTD as a dose with true DLT rate in the target interval [0.16, 0.33]. In scenario 4 (Low-high scenario), the percentage of simulated trials with correctly identified MTD was 68.5%.

In Scenario 2 (high-toxicity scenario), 45.3% of the simulated trials declared a dose as MTD which has its true DLT rate in the targeted toxicity range. However, since in this scenario 80 mg has a DLT probability of 0.34 which is relatively close to the upper bound of the target interval [0.16, 0.33), the BI 836858 dose of 80 mg was quite often determined as MTD, namely in 21.6% of the simulated trials. When considering this as MTD as well, the rate of simulated trials with correctly identified MTDs would add up to 66.9%. Furthermore, in scenario 2, the starting dose has already 0.25 probability of observing a DLT in the first cohort. This contributes to the high percentage (32.6%) of all simulated trials for which the trial is stopped since none of the doses is considered tolerable anymore. This is an expected situation for a high-toxicity scenario.

In scenario 3 (low-toxicity scenario) 29.8% of the simulated trials declared the MTD with true toxicity rate in the target interval and 68.8% declared a MTD with true DLT rate in the underdose interval. This is an expected situation for a low-toxicity scenario.

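### The protocol's count-only criterion permits an MTD to be declared with no DLT while a higher dose still passes overdose control, and the SAP's definition of the MTD can name a different dose from the same data

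*Protocol*

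**What the plan says.** Protocol 7.1.1, repeated in 4.1.3.1, opens the rule with "The MTD may be considered reached if the following criteria are fulfilled" and lists two criteria:

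- Criterion 1: "The posterior probability of the true DLT rate in the target interval [0.16, 0.33] of the MTD is above 0.50, OR"
- Criterion 2: "At least 15 patients have been treated in the study, of which at least 6 were treated at the MTD"

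After each cohort, the model recommends "the level at which the probability for the target dosing interval is maximal out of the dose candidates satisfying the overdose control criterion", where overdose control means P(DLT rate at least 0.33) below 25%. The step is limited: "the maximum allowable dose increment for the subsequent cohort will be no more than 100% of previous dose levels". Stopping is optional: "The SMC may recommend stopping the dose finding phase after the criterion for MTD is fulfilled". If a dose shows no DLT and its efficacy is judged sufficient, the SMC may instead label it the RExP1D.

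Protocol 5.3.3 adds that "the SMC will make a final determination of the RP2D, which must not exceed the MTD". Section 2.2 foresees that the MTD may not be reached.

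SAP 5.1 defines the primary-endpoint MTD in another way: the highest BI 836858 dose, in combination, for which the risk of a true DLT rate above 33% is less than 25%. The 15/6 counts do not appear in SAP 5.1 or 7.4.

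**The concern.** The OR makes criterion 2 sufficient on its own, and its only inputs are two patient counts. DLT data enter only through whichever dose is being considered as the MTD, and criterion 2 does not define that dose: it uses the MTD to decide whether the MTD has been reached. With few or no DLTs, the dose so labelled may be one that the model regards as probably under-dosed, with room above it.

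The MTD is a Phase I primary endpoint, and its name reads as a toxicity limit. Under 5.3.3 it also caps the RP2D. If the label can rest on counts alone, a reader of the report cannot tell an MTD supported by toxicity data from one that marks where enough patients had been treated. The SAP's definition can point to a different dose from the same data, so the reported endpoint depends on which document is followed.

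**Working it through.** **Inputs.** Model and reference doses (160 mg; 20 mg/m²) from Protocol 7.1.1; priors from Table 7.1.1: 3; interaction prior normal with mean 0 and SD 0.993; intervals under [0, 0.16), target [0.16, 0.33), over [0.33, 1]. Doses 20/40/80/160/320 mg are in Table 7.1.1: 4, and 240 mg is the intermediate level in Table 10.2: 1.

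**Formula.** logit(π₁) = log α₁ + β₁ log(d₁/160); logit(π₂) = log α₂ + β₂ log(d₂/20); π⁰ = π₁ + π₂ − π₁π₂; odds(π₁₂) = odds(π⁰) · exp(η · d₁/160 · d₂/20); DLTs binomial. Decitabine is fixed at 20 mg/m². Posterior probabilities come from weighting several million prior draws by the likelihood.

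**The plan's own figures first.**

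| Quantity | Protocol | Recomputed |
|---|---|---|
| Prior P(overdose) at 20, 40, 80, 160, 320 mg | 0.133, 0.186, 0.312, 0.537, 0.665 | 0.135, 0.190, 0.312, 0.538, 0.669 |
| Scenario 12 (0/3 at each of 20, 40, 80, 160 mg): P(overdose) at 160 mg | 0.066 | 0.067 |
| Scenario 12: P(overdose) at 240 mg | 0.210 | 0.207 |

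The model is reproduced to within simulation error.

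**Main example: no DLT in 15 patients, 3/3/3/6 at 20/40/80/160 mg.**

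- Criterion 2 at 160 mg: 3 + 3 + 3 + 6 = 15, and 6 at the dose. Met.
- Criterion 1 at 160 mg: P(under) 0.819, P(target) 0.162, P(over) 0.019. Since 0.162 < 0.50, not met.
- Room above: P(over) is 0.119 at 240 mg (a step of 240/160 − 1 = 50%) and 0.185 at 320 mg (320/160 − 1 = 100%). Both are below 0.25 and within the step limit.
- SAP 5.1 on the same data: the highest listed dose with P(over) < 0.25 is 320 mg, not 160 mg.

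**Is the example reachable?** After 0/9 at 20/40/80 mg the recomputed P(over) at 160 mg is 0.271, so a second cohort at 80 mg may be needed before that step, although the protocol's scenario 12 uses the direct path. Two other zero-DLT data sets do not depend on it:

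| Data (no DLT) | Dose meeting the counts | P(target) there | P(over) at higher doses |
|---|---|---|---|
| 3/3/9 at 20/40/80 mg (N = 15) | 80 mg | 0.134 | 160 mg: 0.170 |
| 3/3/6/6 at 20/40/80/160 mg (N = 18) | 160 mg | 0.134 | 240 mg: 0.109; 320 mg: 0.174 |

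In each, criterion 2 alone is met and a dose within the 100% step passes overdose control.

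**How often.** An illustrative simulation applied the rule literally (cohorts of 3, doses 20/40/80/160/320 mg, 1000 trials per scenario of Table 10.2: 2). An MTD with no DLT, while the next dose still passed, arose in about 9% of trials in the low-toxicity scenario, about 1% in low-high, and under 0.5% in the other two. This is a rough guide: Table 10.2: 3 could not be reproduced, because its simulation rules are not given (mean patients in the low-toxicity scenario about 14 to 15, against 17.21 printed).

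**The case against.** The strongest reply is that this is a discretionary stopping rule, not an estimator. The MTD may be considered reached, the SMC may recommend stopping, and a dose with no DLT has its own label, the RExP1D. That stands: a reader might infer that the primary endpoint automatically returns an MTD, and the documents do not support this. But the discretion has no stated criterion. The RExP1D route is optional and requires sufficient efficacy, and nothing in it blocks criterion 2.

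Second, under SAP 5.1 a dose is not the MTD while a higher candidate has less than 25% overdose risk. That is correct, and it is the conflict itself: the SAP does not say that its definition overrides 7.1.1. The SAP definition would also name a dose with no DLT at all.

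Third, Table 10.2: 3 prints at least one DLT in every simulated trial. Under the low-toxicity rates the zero-DLT path 3/3/6/6 has probability 0.94³ × 0.90³ × 0.88⁶ × 0.82⁶ = 0.085, so a rule that stopped there would have shown some trials with none. The simulated rule may therefore differ from the written one. This is an inference, and it makes clarification more necessary. The appendix does disclose the under-dosing ("68.8% declared a MTD with true DLT rate in the underdose interval. This is an expected situation for a low-toxicity scenario"), but has no category for an MTD not reached.

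Fourth, Phase II was cancelled, so the RP2D cap governs nothing further in this trial. That limits the consequence to how the primary endpoint is reported.

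Two further inferences should be resisted:

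- The 16 escalation and 33 extension patients do not make criterion 2 close to automatic. The description of amendment 6 gives these as actual numbers. Protocol 4.1.2 assigns extension patients after the MTD or RExP1D is determined, and Cohort B uses the other decitabine schedule.
- Simulating a true DLT rate of zero gives no stable headline. At 0/18 (3/3/6/6), P(target) is practically tied at 160 mg and 320 mg (0.134 and 0.135), so the recommended dose depends on Monte Carlo noise. If 240 mg is on the grid (0.155) it is recommended, with nobody yet treated there.

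**Conclusion.** The point holds as a conflict between two stated rules for a primary endpoint. Criterion 2 is sufficient alone, contains no toxicity condition, and permits an MTD declaration with no DLT while a higher permitted dose passes overdose control. In the 0/15 example the dose so labelled has P(underdose) 0.82 and P(target) 0.16, and the SAP definition points elsewhere. Section 2.2 allows for an MTD not reached, but no analysis text says when to report it.

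The conclusion rests on three assumptions: the priors are those in Table 7.1.1: 3 (the protocol allows them to be updated); 160 mg is taken as the MTD candidate in criterion 2 (it is the highest dose tested, and on the five-dose grid the one with the largest P(target) among doses passing overdose control, although 240 mg would be recommended if listed, 0.171 against 0.162); and 240 and 320 mg count as candidates under SAP 5.1. Nothing here concerns the DLTs actually observed, and no dose is recommended.

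**What to change.** Reconcile Protocol 4.1.3.1 and 7.1.1 with SAP 5.1 and 7.4:

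- Keep 15/6 as permission for the SMC to stop escalation.
- Report the MTD as reached only if (a) P(target) at that dose exceeds 0.50, or (b) the 15/6 counts are met and the next higher dose allowed by the 100% rule fails the overdose criterion.
- Otherwise report the MTD as not reached, with the highest dose studied, its DLT count and its posterior interval probabilities.
- Say which dose criterion 2 means by the MTD, which doses count as candidates in SAP 5.1, and what applies when no higher candidate is left.
- In 10.2, state the simulated stopping rule and how often each scenario ends with no MTD reached.

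The cost is a few sentences and the rerun of the operating characteristics. The posterior probabilities come from the BLRM already in use, and no extra patients are needed. The one real downside is that the primary endpoint may be reported as not reached.
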